REPETITIVE TRANSCRANIAL MAGNETIC STIMULATION (RTMS) FOR OBSESSIVE-COMPULSIVE DISORDER (OCD)

Regulatory Sponsor (S-I): [name], PhD
Co-Investigator: [name]
Study Product: Brainsway™ cingulate coil (HAC coil)
Protocol Number: AAAQ8771

Study Summary

Title	Repetitive Transcranial Magnetic Stimulation (TMS) for Obsessive-Compulsive Disorder (OCD)
Short Title	rTMS for OCD
Protocol Number	Initial version
Methodology	Open-label study to investigate the feasibility and effectiveness of administering rTMS to patients suffering from OCD.
Study Duration	Study duration will be 3 weeks
Study Center(s)	Single-center
Objectives	The goal of the study is to assess whether repetitive transcranial magnetic stimulation (rTMS) can be used as a non-invasive option to benefit patients suffering from Obsessive Compulsive Disorder (OCD)
Number of Subjects	15
Diagnosis and Main Inclusion Criteria	Obsessive-compulsive disorder
Study Product and Planned Use	Brainsway™ HAC-coil to target the cingulate cortex
Reference therapy	N/A
Statistical Methodology	Statistics will be computed to observe changes within subjects and between subjects to assess the effectiveness of rTMS

1 Introduction

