3.1 General Design

rTMS delivery: High-frequency (10 Hz) deep TMS will be administered at the dACC to patients over 3 weeks using the HAC-coil (Brainsway™ cingulate coil) designed specifically to target the cingulate cortex and the Magstim Rapid stimulator (Magstim Company Limited, Whitland, UK). Sessions will be administered five times a week with a total of 15 visits. The intensity of stimulation will be relative to resting motor threshold (110%). Forty 3-second trains with an inter-train period of 20 seconds will be applied. Total number of pulses administered will be 1200. Periodic weekly behavioral assessments will be performed with the Yale-Brown Obsessive Compulsive Scale (Y-BOCS) to monitor OCD symptoms. We will also test for suicidal ideation (C-SSRS) and monitor manic symptoms (YMRS) twice a week in addition to baseline and at the end of treatment course (x 8 total) and test cognitive function with Minimental status examination (MMSE). Subjects will be compensated for their daily visits in order to offset inconvenience related to time, effort and transportation costs. They will receive \$100 per fMRI session (x2 total) plus \$40 per TMS session (x15 total) over the study period.

Neuropsychological scales and tests: Neuropsychological evaluations will be administered at baseline and at the end of the study.

1. Scales (expected to take 30-40 minutes total):

- USP-Sensory Phenomena Scale

- Hamilton Depression Rating Scale
- Hamilton Anxiety Rating Scale
- Beck Anxiety Inventory
- Beck Depression Inventory, 2nd Edition
- Sheehan Disability Scale
- Barratt Impulsiveness Scale (BIS -11)
- Clinical Global Impression (CGI)
- Quality of Life Enjoyment and Satisfaction- short form (Q-LES)

2. Neuropsychological measures (expected to take about 90 minutes and can be performed in separate sessions as needed):

- Wechsler Abbreviated Scale of Intelligence (WASI)
- WMS-III Faces, LM, Digit Span, Spatial Span, LNS
- Rey Osterrieth Complex Figure (ROCF)
- California Verbal Learning Test, 2nd Edition (CVLT-II)
- Iowa Gambling Test (IGT)
- Wisconsin Card Sort Task (WCST)
- Judgment of Line Orientation
- Boston Naming Test
- DKEFS Verbal Fluency, Trails, Color Word Interference Test
- Grooved Pegs

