Additionally, pre-rTMS and post-rTMS high-density scalp EEG data (128 channels) will be acquired two times a week for a total of 12 EEG acquisitions. The patient will be engaged in the MSIT during EEG acquisitions. EEG analysis will be used to quantify acute effects of rTMS by exploring within-session data,

and longitudinal effects of rTMS by exploring between-session data. The high-density acquisition will also allow for a thorough analysis in sensor and source domains.

Data Analysis: fMRI regressors will be constructed at multiple offsets in the epoched EEG data to view the temporal progression of the discriminating components (Walz 2013). Linear classifiers will be trained on EEG data to estimate a set of spatial weights to maximize discrimination of 2 conditions. Regressors will also account for single-trial variability. Lastly, we will compute ICA-based source localization on the fMRI data to extract the nodes of the underlying network evoked during this task.

For the EEG analysis, we will first analyze the data in sensor domain and assess the effect of rTMS by computing differences in ERPs and midline frontal theta. This initial analysis will then be used to reconstruct source signal. Region-specific measures (power) and connectivity measures (frequency-dependent coherence) will also be computed. Although EEG measures correspond to a fraction of total synaptic action in a particular tissue volume, strong correlations have been reported between cognitive processing and event-related potentials that occur due to interactions with background synaptic action fields. Therefore, by extending our measures from source activity to source connectivity, we can indirectly measure changes in synaptic plasticity.

Each patient will serve as their own control and statistical comparisons will be made between measures at baseline and at the end of the TMS protocol (3 weeks). Although this study design doesn't address time-effects, we believe it is a crucial first step towards a better understanding of the effects of TMS.

Effectiveness Variables:

- 1) Changes in midline frontal theta and ERPs will be compared pre and post rTMS for OCD
- 2) Changes in dACC connectivity with frontal regions (DLPFC and OFC) will be assessed over the course of rTMS treatment for OCD
- 3) Changes in YBOCS will be assessed over the course of rTMS as a measure of secondary effectiveness. Clinical response will be defined as 35% reduction in YBOCS from baseline.

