3.2 Primary Safety Endpoints

According to the safety guidelines recommended by Brainsway™ corresponding to the HAC coil, 3 weeks is an acceptable study duration with the investigational HAC-coil. Brainsway™ has performed studies in control subjects and in subjects with clinical conditions (MDD, schizophrenia, bipolar disorder, addiction, PTSD) (Brainsway, Ltd. Unpublished data). They have currently tested 209 subjects (98 without concomitant psychotropic medication; 111 with psychotropic medication) with high-frequency, high-intensity rTMS. Of the subjects who were still taking psychotropic medications that could lower seizure thresholds, 3 suffered a seizure. Should the patient experience adverse effects prior to completion of study, their participation will be discontinued in lieu of their safety. Additionally, we will account for the incidence, severity and frequency of all Adverse Events (AEs), including seizures and suicidality (i.e., suicide attempts and completed suicides).

4 Subject Selection and Withdrawal

CRITERION	METHOD OF ASCERTAINMENT
Inclusion:	
1) Male or female outpatients, 18 to 65 years of age.	Self report
2) Primary diagnosis of Obsessive Compulsive Disorder, as confirmed by the Structured Clinical Interview for the DSM-V-TR (SCID).	SCID, DSM-IV-TR

3) Subjects should have at least a moderate level of OCD severity as defined by a Yale-Brown Obsessive Compulsive Disorder Scale (YBOCS) score of greater than 10 on either obsession section or compulsion section (YBOCS-O \geq 10 or YBOCS-C \geq 10).	YBOCS
3) Patients currently on OCD medication must be at the same stable dose(s) and be willing to continue the same dose(s) through the duration of the study. Note: Subjects should be maintained on SSRI medications (with or without additional antidepressant or psychotropic augmentation for treatment of OCD) at a stable therapeutic dosage for at least 2 months prior to study entry and for the duration of the trial, and/or subjects are maintained on psychotherapeutic behavioral intervention therapy (subjects undergoing CBT treatment must be in the maintenance stage and not in the assessment or skills acquisition or training stages).	Physician Evaluation
4) Patients must continue to be under the care of their treating psychiatrist who will be writing prescriptions for concomitant medications through the duration of the study.	Physician Evaluation
5) Capable and willing to provide informed consent	Physician Evaluation

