5.4.2 Storage

The stimulation set-up is currently housed at the New York State Psychiatric Institute on the third floor. Trained investigators or physicians will have access to the setup and will administer the stimulation. A physician will be present during rTMS sessions to ensure patient safety.

6 Study Procedures

	Monday	Tuesday	Wednesday	Thursday	Friday
Baseline	Neuroimaging, Neurophysiology and Neuropsychiatry evaluations				
Week 1	rTMS	rTMS preTMS EEG postTMS EEG MMSE, YMRS,CGI, CSSRS	rTMS	rTMS preTMS EEG postTMS EEG YBOCS, MMSE, YMRS, CGI, CSSRS	rTMS
Week 2	rTMS	rTMS preTMS EEG postTMS EEG MMSE, YMRS, CGI, CSSRS	rTMS	rTMS preTMS EEG postTMS EEG YBOCS, MMSE, YMRS, CGI, CSSRS	rTMS
Week 3	rTMS	rTMS preTMS EEG postTMS EEG MMSE, YMRS, CGI, CSSRS	rTMS	rTMS preTMS EEG postTMS EEG YBOCS, MMSE, YMRS, CGI, CSSRS	rTMS
Follow-up	Neuroimaging, Neurophysiology and Neuropsychiatry evaluations				

7 Statistical Plan

Statistical analyses with time series data and factor analysis will be carried out both within subject (to assess reliability of the observed effects across trials) and across subjects (to assess the generalizability across participants). Sample sizes are chosen based on expected effect sizes and the large heterogeneity in this subject population.

8 Safety and Adverse Events

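### The plan does not say how patients discontinued under its own rules enter the Y-BOCS change and the 35% response rate; by default both rest on completers and may overstate benefit.

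*Combined protocol and SAP*

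**What the plan says.** Under Data Analysis, Section 3.1 makes each patient their own control and states that "statistical comparisons will be made between measures at baseline and at the end of the TMS protocol (3 weeks". Under Effectiveness Variables it adds: "Changes in YBOCS will be assessed over the course of rTMS as a measure of secondary effectiveness". The same item continues: "Clinical response will be defined as 35% reduction in YBOCS from baseline". It does not say at which visit response is judged, or out of how many patients.

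Data between the two end points are planned. Section 3.1 states: "Periodic weekly behavioral assessments will be performed with the Yale-Brown Obsessive Compulsive Scale (Y-BOCS) to monitor OCD symptoms". The Section 6 schedule places these ratings on Thursday of weeks 1, 2 and 3. EEG is recorded twice a week, partly to study "longitudinal effects of rTMS by exploring between-session data". Section 7 mentions time series analyses.

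Several sections take patients off treatment or out of the study. Section 3.2 says: "Should the patient experience adverse effects prior to completion of study, their participation will be discontinued in lieu of their safety". Section 1.5.1 ends participation for suicidal ideation or manic symptoms. Section 4 lists, among other reasons, seizure, raised suicide risk, a clinically significant adverse event and withdrawn consent. Section 8.4 stops rTMS for any adverse event. After discontinuation, Section 4 leaves safety to the patient's own physician and mentions no outcome assessment. Neither Section 3.1 nor Section 7 defines an analysis set or a rule for missing data.

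**The concern.** A baseline-to-end comparison needs an end value. A patient removed in week 1 or 2 has none, and the plan does not say what happens to that patient's record. If nothing more is specified, the end-of-course change and the response rate are computed in those who finished.

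Finishing is not neutral here. Some removal triggers are intolerance, and others (suicidality, manic symptoms) are psychiatric deterioration. If such patients also do worse on Y-BOCS, leaving them out makes rTMS look better than it was in those who started it. With 15 patients and no control arm, a few losses matter. An open denominator also allows the choice to be made after the data are seen.

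**Working it through.** **1. The plan's own figure.** The study summary gives "Number of Subjects 15". Section 7 gives the basis: "Sample sizes are chosen based on expected effect sizes and the large heterogeneity in this subject population". No effect size, SD, significance level, power, response rate or dropout rate is stated, so 15 cannot be reproduced. Nothing below shows a stated figure to be wrong.

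**2. What a patient stopped mid-course contributes.**

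| Measure | When taken (Sections 3.1 and 6) | Available if stopped early |
|---|---|---|
| Y-BOCS | Baseline; Thursday of weeks 1, 2, 3 | Ratings up to the stop; none after baseline if stopped before Thursday of week 1 |
| 128-channel EEG | Twice weekly, before and after rTMS | Sessions up to the stop |
| fMRI-EEG, structural MRI, DTI | Baseline and end | Baseline alone |
| Neuropsychological tests | Baseline and end | Baseline alone |

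Partial Y-BOCS data can therefore exist, but no rule brings them into the week-3 change or the response rate. For imaging and neuropsychological tests there is nothing between the two end points to use.

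**3. Response rate.** Inputs: N = 15 (study summary); r responders, all among completers, and d discontinuations (both assumed). Completer rate = r/(15 − d). All-treated rate with discontinued patients counted as non-responders = r/15. With r = 5:

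| d | Completers | All treated | Difference (points) |
|---|---|---|---|
| 1 | 5/14 = 35.7% | 5/15 = 33.3% | 2.4 |
| 3 | 5/12 = 41.7% | 33.3% | 8.3 |
| 5 | 5/10 = 50.0% | 33.3% | 16.7 |

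The exact (Clopper-Pearson) 95% interval for 5/15 is 11.8% to 61.6%. For r from 4 to 6, the difference is 1.9 to 2.9 points at d = 1, 6.7 to 10.0 at d = 3, and 13.3 to 20.0 at d = 5.

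**4. Direction.** Take r = 5 and d = 3.
- If none of the three would have responded, the all-treated rate is 5/15 = 33.3%, below the completers' 41.7%.
- If they would have responded at the completers' rate, it is (5 + 3 × 5/12)/15 = 6.25/15 = 41.7%, and there is no bias.
- If all three would have responded, it is 8/15 = 53.3%, and the completer rate understates.

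**5. Mean change.** With completer mean m and mean c in those discontinued, the all-treated mean is [(15 − d)m + dc]/15. If c = 0, this is (15 − d)/15 of m: 0.93, 0.80 and 0.67 for d = 1, 3 and 5. If c = m, the two agree.

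**6. How likely any loss is.** For an assumed discontinuation probability p, the chance of at least one among 15 is 1 − (1 − p)^15: 54% at p = 5%, 79% at 10% and 96% at 20%.

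**The case against.** A reader might infer that the plan uses two time points and nothing else, and throws the weekly scores away. The documents do not support that. Y-BOCS change is to be assessed over the course of treatment, EEG is compared between sessions, and Section 7 refers to time series. What is missing is any statement of how those interim values enter the end-of-course estimate or the response rate.

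A reader might also infer that the sponsor has chosen a completers-only analysis. No section says so. It is what follows if the stated contrast is computed with no further rule.

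Finally, a reader might infer that the result is bound to favour rTMS by a calculable amount. No removal rule mentions Y-BOCS or lack of response. Several triggers, such as pregnancy, tremor or failure to find a motor threshold, need not track OCD severity, and a stop for headache need not either. A percentage for the overstatement of mean change would need an assumed link between withdrawal and Y-BOCS that the documents do not supply.

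It is also fair that Y-BOCS is a secondary measure in a 15-patient, open-label, single-centre study. That lowers the stakes. It does not fill the gap, since effectiveness is among the study's stated aims.

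**Conclusion.** The concern holds as a gap in specification with a plausible bias. The plan states a baseline-to-end contrast and a response threshold, removes patients for reasons partly tied to tolerability and psychiatric state, and does not say how they are counted. Upward bias is the more plausible direction, because several rules select on intolerance or worsening, but it is not established. If withdrawal is unrelated to Y-BOCS the expected bias is about zero, and it reverses if those removed would have done better than completers.

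The size depends on two quantities that the documents do not give: the number of responders and the number of discontinuations. Under the assumptions in the working, the response rate moves by about 2 points with one loss and by 13 to 20 points with five. The exact interval for 5 of 15 is wide in any case, so the main gain from a fix is a denominator set in advance and a result that describes everyone treated.

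**What to change.** In Sections 3.1 and 7, state that:

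1. The analysis set is every patient who receives at least one rTMS session.
2. Y-BOCS change at week 3 is estimated from a repeated-measures model using baseline and all weekly ratings, including those of patients who later stop.
3. Response is judged at a named visit, for example the last scheduled rating (Thursday of week 3). The denominator is all treated patients, a missing end-of-course Y-BOCS counts as non-response, and an exact 95% interval is given.
4. Completer results are shown as a sensitivity analysis, and discontinuations are reported with reasons. Change in fMRI, DTI and the neuropsychological measures taken only at baseline and end is labelled as a completer result.

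Sections 1.5.1, 3.2, 4, 5.2 and 8.4 must also be reconciled. Sections 3.2 and 8.4 read as applying to any adverse effect. Section 1.5.1 describes headache as managed with over-the-counter medicine, Section 4 refers to a clinically significant event, and Section 5.2 allows reduced intensity for poor tolerance. These rules determine how many patients lack end data.

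The cost is a few sentences and no new data. The response rate will be lower, by an amount that depends on the number of discontinuations; counting missing as non-response is a conservative convention and understates response if some of those removed did respond. The repeated-measures model assumes that withdrawal is explained by the observed scores, which may fail if patients leave for worsening that Y-BOCS does not capture.

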3.2 Primary Safety Endpoints

According to the safety guidelines recommended by Brainsway™ corresponding to the HAC coil, 3 weeks is an acceptable study duration with the investigational HAC-coil. Brainsway™ has performed studies in control subjects and in subjects with clinical conditions (MDD, schizophrenia, bipolar disorder, addiction, PTSD) (Brainsway, Ltd. Unpublished data). They have currently tested 209 subjects (98 without concomitant psychotropic medication; 111 with psychotropic medication) with high-frequency, high-intensity rTMS. Of the subjects who were still taking psychotropic medications that could lower seizure thresholds, 3 suffered a seizure. Should the patient experience adverse effects prior to completion of study, their participation will be discontinued in lieu of their safety. Additionally, we will account for the incidence, severity and frequency of all Adverse Events (AEs), including seizures and suicidality (i.e., suicide attempts and completed suicides).

4 Subject Selection and Withdrawal

CRITERION	METHOD OF ASCERTAINMENT
Inclusion:	
1) Male or female outpatients, 18 to 65 years of age.	Self report
2) Primary diagnosis of Obsessive Compulsive Disorder, as confirmed by the Structured Clinical Interview for the DSM-V-TR (SCID).	SCID, DSM-IV-TR

3) Subjects should have at least a moderate level of OCD severity as defined by a Yale-Brown Obsessive Compulsive Disorder Scale (YBOCS) score of greater than 10 on either obsession section or compulsion section (YBOCS-O \geq 10 or YBOCS-C \geq 10).	YBOCS
3) Patients currently on OCD medication must be at the same stable dose(s) and be willing to continue the same dose(s) through the duration of the study. Note: Subjects should be maintained on SSRI medications (with or without additional antidepressant or psychotropic augmentation for treatment of OCD) at a stable therapeutic dosage for at least 2 months prior to study entry and for the duration of the trial, and/or subjects are maintained on psychotherapeutic behavioral intervention therapy (subjects undergoing CBT treatment must be in the maintenance stage and not in the assessment or skills acquisition or training stages).	Physician Evaluation
4) Patients must continue to be under the care of their treating psychiatrist who will be writing prescriptions for concomitant medications through the duration of the study.	Physician Evaluation
5) Capable and willing to provide informed consent	Physician Evaluation
6) Signed HIPAA authorization	Physician Evaluation
Exclusion:	
1) Investigators, and their immediate families (defined as spouse, parent, child or sibling, whether by birth or legal adoption).	Self Report
2) Individuals diagnosed by the investigators with the following conditions: Bipolar Disorder (lifetime), any Psychotic Disorder (lifetime), history of substance abuse or dependence within the past year (expect nicotine and caffeine).	Physician Evaluation, SCID, DSMIV-TR
3) An Axis II Personality Disorder, which in the judgment of the investigator may hinder the patient in completing the procedures required by the study protocol.	Physician Evaluation, Private Psychiatrist Reports
4) Individuals with a clinically defined neurological disorder including, but not limited to: stroke, tics, space occupying brain lesion, any history of seizures except those therapeutically induced by ECT, history of cerebrovascular accident, transient ischemic attack within two years, cerebral aneurysm, dementia, Parkinson's Disease, Huntington Chorea, Multiple Sclerosis.	Physician Evaluation, Medical Records
5) Increased risk of seizure for any reason, including prior diagnosis of increased intracranial pressure (such as after large infarctions or trauma), or history of significant head trauma with loss of consciousness for \geq 5 minutes.	Patient Reports
6) History of treatment with rTMS therapy for any disorder.	Patient Reports

Subjects with positive responses to the Transcranial Magnetic Stimulation Adult safety screen (TASS, enclosed)	TASS
7) History of treatment with Deep Brain Stimulation.	Patient Reports
8) Use of any investigational drug within 12 weeks of the randomization visit.	Patient Reports
9) Current use of any medications with proconvulsive action, such as bupropion, maprotiline, tricyclic antidepressant, clomipramine, classical antipsychotics.	Physician Evaluation, Medical Records
10) Inability to obtain a motor threshold in patients due to chronic use of a medication (eg. anticonvulsants, benzodiazepines, sedative/hypnotics and atypical antipsychotics)	Physician Evaluation, Medical Records
11) Significant acute suicide risk, based on the current state or recent history using Columbia Suicide Severity Rating Scale (CSSRS).	C-SSRS
12) Cardiac pacemakers, implanted medication pumps, intracardiac lines, or acute, unstable cardiac disease.	Physician Evaluation
13) Intracranial implants (e.g. aneurysm clips, shunts, stimulators, cochlear implants, or electrodes) or any other metal object within or near the head, excluding the mouth, that cannot be safely removed.	Physician Evaluation
14) If participating in psychotherapy, must have been in stable treatment for at least three months prior to entry into the study, with no anticipation of change in frequency of therapeutic sessions, or the therapeutic focus over the duration of the rTMS trial.	Private Psychiatrist Reports
15) Current illicit drug use.	Physician Evaluation and urine drug screen
16) Current significant laboratory abnormality. Note: Clinically significant laboratory abnormality refers to patient lab results that fall outside the established normal ranges, may be indicative of the presence of a medical condition, and are not thought to reflect an artifact or routine lab error (e.g. hemolysis). Results of laboratory tests are reviewed by the study physician prior to any treatment. Abnormal lab results of clinical significance that cannot be resolved (e.g. by repeating the test to rule out laboratory error or poor quality of the original sample) will lead to exclusion from the study.	Physician Evaluation
17) Known or suspected pregnancy.	Urine pregnancy test
18) Women who are breast-feeding.	Self Report
19) Women of childbearing potential not using a medically accepted form of contraception when engaging in sexual intercourse.	Self Report

Patient Discontinuation:

A subject will be discontinued from the study for any of the following reasons:

- Inability to locate and quantify a motor threshold (MT) as defined in the protocol.
- The investigator decides that the patient should be withdrawn for the safety and welfare of the patient. For example, the patient experiences a clinically significant adverse event that is inconsistent with continuation in the study.
- The patient withdraws consent.
- Subject has significant tremor in any limb.
- Subject experiences a seizure.
- Subject has an elevated risk of suicide, based on results from the Columbia Suicide Severity Rating Scale (C-SSRS) and/or psychiatric interview or attempts suicide after receiving rTMS. The study investigator should refer the subject to his/her primary psychiatrist or inpatient hospitalization in case the patient is discontinued from the study.
- Subject becomes pregnant.

The safety of the patient following their discontinuation will be ensured by their primary physician.

5 Study Device

